#### 5.1.2 Subject Inclusion Criteria

In order to be eligible for participation in this trial, the subject must:

- 1. Have histologically or cytologically-confirmed head and neck squamous cell carcinoma of the oral cavity (excluding lip), oropharynx, hypopharynx, or larynx.
- 2. Have TNM clinical stage III, IVA, or IVB disease. Can have T0 disease if evaluation of pathology indicates an origin of one of the above sites. (See criteria 1)
- 3. Be eligible for curative-intent concurrent chemoradiation therapy
- 4. Be willing and able to provide written informed consent for the trial.
- 5. Be  $\geq$  18 years of age on day of signing informed consent.
- 6. Have a known p16 status by immunohistochemical stain
  - a. HPV positivity is defined by p16 IHC staining of > 70% of tumor cells (strong and diffuse nuclear and cytoplasmic staining)
  - b. For cases that are indeterminate or if p16 testing cannot be accurately performed, HPV positivity can be confirmed by high-risk HPV DNA Testing which covers the following HPV subtypes: 16, 18, 31, 33, 35, 39, 45, 51, 52, 56, 58, 59, 66, 68.
- 7. Have measurable disease based on RECIST 1.1
- 8. Be willing to provide tissue from a recently obtained core or excisional biopsy of a tumor lesion. *Recently-obtained is defined as a specimen obtained up to 60 days prior to enrollment. Subjects for whom recently-obtained samples cannot be provided (e.g. inaccessible or subject safety concern) may submit an archived specimen only upon agreement from Sanford Research.*
- 9. Have a performance status of 0 or 1 on the ECOG Performance Scale.

10. Demonstrate adequate organ function as defined in Table 1, all screening labs should be performed within 10 days of treatment initiation (Day -7).

System	Laboratory Value		
Hematological			
Absolute neutrophil count (ANC)	≥1,500 /mcL		
Platelets	≥100,000 / mcL		
Hemoglobin	$\geq$ 9 g/dL or $\geq$ 5.6 mmol/L without transfusion or EPO dependency (within 7 days of assessment)		
Renal			
Serum creatinine OR Measured or calculated a creatinine	$\leq 1.5 \text{ X upper limit of normal (ULN) } \underline{OR}$		
clearance	$\geq$ 60 mL/min for subject with creatinine levels > 1.5 X		
(GFR can also be used in place of creatinine or CrCl)	institutional ULN		
Hepatic			
Serum total bilirubin	≤ 1.5 X ULN OR		
	Direct bilirubin ≤ ULN for subjects with total bilirubin levels > 1.5 ULN		
AST (SGOT) and ALT (SGPT)	$\leq$ 2.5 X ULN OR $\leq$ 5 X ULN for subjects with liver metastases		
Albumin	≥2.5 mg/dL		

Table 1 Adequate Organ Function Laboratory Values

- 11. Female subject of childbearing potential should have a negative urine or serum pregnancy within 72 hours prior to receiving the first dose of study medication. If the urine test is positive or cannot be confirmed as negative, a serum pregnancy test will be required.
- 12. Female subjects of childbearing potential should be willing to use 2 methods of birth control or be surgically sterile, or abstain from heterosexual activity for the course of the study through 120 days after the last dose of study medication (Reference Section 5.7.2). Subjects of childbearing potential are those who have not been surgically sterilized or have not been free from menses for > 1 year.
- 13. Male subjects should agree to use an adequate method of contraception starting with the first dose of study therapy through 120 days after the last dose of study therapy.

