# 5.2.1.2.2 Dose Modification for Cisplatin

Investigators must use cisplatin for this protocol. Substitutions to carboplatin will not be permitted. If toxicities occur, dose reductions as outlined in Tables 3.1 and 3.2 should be performed.

Cisplatin will not be given until the ANC exceeds 1000/mm3 and the platelet count exceeds 75,000/mm3. Myeloid growth factors can be used per local guidelines.

Complete blood count, differential and platelets will be checked weekly during therapy. Cisplatin dose will be reduced for nadir WBC or platelet count as follows:

Nadir			% of 100%
ANC		Platelet	Cisplatin Dose to
			Give
> 1000	And	>75,000	100% (dose level 0)
500 - 999	Or	50-75,000	80% (dose level -1)
< 500	Or	< 50,000	60% (dose level -2)

Table 3.1 - Cisplatin modifications based on Hematology Parameters

Cisplatin will only be given if the serum creatinine is < 1.6 mg/dl. Reduce cisplatin dose for transient rises in creatinine as follows:

 Table 3.2 Cisplatin modifications based on Creatinine Peak

Creatinine Peak	Cisplatin Dose to Give
≤ 1.6	100% (dose level 0)
>1.6-4.0	80% (dose level -1)
> 4.0	60% (dose level -2)

In individuals whose creatinine does not come back down to <1.6 mg/dl, cisplatin should continue to be held.

Neurotoxicity:

Grade 3 hearing loss in the speech frequency range is an indication to discontinue cisplatin. Significant (grade 3) myopathy, weakness, or neuropathy; seizure or paralysis should prompt discontinuation of cisplatin and contact with the principal investigator.

Other adverse events:

Any other grade 4 adverse events, not previously outlined above, will result in decreasing the next weekly dose of cisplatin to 80% (dose level -1). If any grade 4 event persists beyond dose reduction to 60% (dose level -2), cisplatin will be permanently discontinued for the duration of the study.

Dose reductions for grade 3 events, not previously outlined above, will be permitted, but are at the discretion of the individual treating physician. Dose modifications should be performed as: Dose level -1 = 80% dose, Dose level -2 = 60% dose, dose level -3 = hold further cisplatin. Treatment-related grade 3 mucositis, skin toxic effects, xerostomia, dysphagia, and anorexia, are expected toxicities, and dose reduction is not recommended, but will be permitted.

Dose re-escalations are not permitted.

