#### 5.6.2 **Prohibited Concomitant Medications**

Subjects are prohibited from receiving the following therapies during the Screening and Treatment Phase of this trial:

- Antineoplastic systemic chemotherapy or biological therapy
- Immunotherapy not specified in this protocol
- Chemotherapy not specified in this protocol
- Investigational agents other than pembrolizumab
- Radiation therapy not specified in this protocol
- Live vaccines within 30 days prior to the first dose of trial treatment and while participating in the trial. Examples of live vaccines include, but are not limited to, the following: measles, mumps, rubella, varicella/zoster, yellow fever, rabies, BCG, and typhoid vaccine.
- Systemic glucocorticoids for any purpose other than to modulate symptoms from an event of clinical interest of suspected immunologic etiology. The use of physiologic doses of corticosteroids may be approved after consultation with the study Principal Investigator or designee.

Subjects who, in the assessment by the investigator, require the use of any of the aforementioned treatments for clinical management should be removed from the trial. Subjects may receive other medications that the investigator deems to be medically necessary.

The Exclusion Criteria describes other medications which are prohibited in this trial.

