# 6.3 Follow-up

		Months Following Study Treatment End (after day 150 imaging)								
Follow-up Month	Follow up visit 1 (90 days from Day 150)	Follow up visit 2 (90 days from FU-V1)	Follow up visit 3 (180 days from FU-V2)	Follow up visit 4 (180 days from FU-V3)	Follow up visit 5 (180 days from FU-V4)	Follow up visit 6 (352 days from FU-V5)	Follow up visit 7 (352 days from FU-V6)	Follow up visit 8 (352 days from FU-V7)	Study End	
Scheduling Window	+/- 14 days	+/- 30 days	+/- 30 days	+/- 30 days	+/- 30 days	+/- 30 days	+/- 30 days	+/- 30 days		
Administrative Procedures									]	
Subsequent antineoplastic therapy status	x	X	X	X	X	x	X	X		
Survival Status 	X	x	x	x	x	x	x	X	-	
Clinical Procedures and Asses	sments				I		I		1	
Adverse Events 	x	X	X	X	x	x	x	x	-	
Directed Physical Exam	x	x	X	X	x	X	x	x		
Vitals and Weight (optional)	x	x	X	X	x	X	x	x		
ECOG PS(optional)	X	x	x	X	X	X	X	X		

	Months Following Study Treatment End (after day 150 imaging)								
Follow-up Month	Follow up visit 1 (90 days from Day 150)	Follow up visit 2 (90 days from FU-V1)	Follow up visit 3 (180 days from FU-V2)	Follow up visit 4 (180 days from FU-V3)	Follow up visit 5 (180 days from FU-V4)	Follow up visit 6 (352 days from FU-V5)	Follow up visit 7 (352 days from FU-V6)	Follow up visit 8 (352 days from FU-V7)	Study End
Scheduling Window	+/- 14 days	+/- 30 days	+/- 30 days	+/- 30 days	+/- 30 days	+/- 30 days	+/- 30 days	+/- 30 days	
Laboratory Procedures/Assess	nents (local labor	atory testing):							
CBC with differential	x	x	x	x	x	X	x	x	-
Serum Chemistry Panel 	X	x	x	X	x	X	x	x	-
T3, FT4, TSH		x	X	X	X	X	x	x	
Imaging									-
Tumor Imaging (CT neck)	X	x	x		x	x	x	x	-
Correlative Study Procedures	 	I	 						
Blood for correlative studies 			x						
Patient Reported Outcomes (PI	RO)				 			 	
FACT H&N 			x		x				

1. Treatment day 1 coincides with the first day of radiation therapy. Any treatment days before will be denoted with a preceding (-) symbol.

2. The window for each visit is outlined as above. If a treatment is delayed, the following treatment must occur with the same delay. Additional treatment delay can occur with the specified scheduling window. If treatment is delayed beyond that window, treatment for that scheduled course must be held. Treatment can be resumed for the next scheduled treatment day.

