13. Patients with residual disease (SD, PR, or PD) on post-treatment imaging will undergo salvage surgical resection (at the discretion of the surgeon) if their disease is felt curable with salvage surgery. Additionally, patients with a CR and clinical suspicion for viable residual disease will be offered salvage surgery. Following pathology analysis, salvage surgical tissue will be sent for correlative studies. Detailed instructions for tissue collection, processing, and shipment are included in the procedures manual.

14. PET imaging at baseline and treatment end is not required for the study, but is allowed for use to determine complete response rate when tumor response on standard imaging cannot confirm CR based on RECIST 1.1. Please see sections 7.1.2.6.2 and 7.1.2.6.3 for details.

15. Screening labs completed within 7 days (168 hours) of treatment initiation (day -7) will not need to be repeated.

16. Once a subject experiences confirmed disease progression or starts a new anti-cancer therapy, the subject moves into the Survival Follow-Up Phase. These subjects will be followed every 6 months to assess for survival status until death, withdrawal of consent, or the end of the study, whichever occurs first.

17. If a subject discontinues pembrolizumab, return visit timing is left to treating physician discretion until day 150 although it is highly recommended that the subject return for Day 78, 120, and 150 so research specimens and QOL can be collected.

18. Minimum interval between pembrolizumab doses is 14 days.

19. Vital signs and weight do not need to occur on the same day as the visit but need to be completed within the window and prior to the next treatment.

20. Once a subject transitions to follow-up all documented AEs will be followed until resolution or to a new baseline as determined by the treating investigator. Only new AEs that could be considered an ECI or irAR will be documented and followed while in follow-up.

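### The renal entry criterion in Table 1 is looser than the protocol's own cisplatin limit, so a patient can qualify, receive the Day -7 pembrolizumab dose and then have cisplatin held

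*Combined protocol and SAP*

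**What the plan says.** **Entry.** The renal row of Table 1 (section 5.1.2) can be met in two ways: serum creatinine no higher than 1.5 times the upper limit of normal (ULN), or clearance of at least "60 mL/min for subject with creatinine levels > 1.5 X" institutional ULN. GFR may stand in for either measure. No ULN is given in mg/dL, and the clearance route has no upper bound on creatinine.

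**Dosing.** Section 5.2.1.2.2 uses an absolute limit: "Cisplatin will only be given if the serum creatinine is < 1.6 mg/dl". It then says: "In individuals whose creatinine does not come back down to <1.6 mg/dl, cisplatin should continue to be held". Clearance plays no part in this rule. The same section states: "Substitutions to carboplatin will not be permitted".

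**Order of treatment.** Section 5.2 starts pembrolizumab on Day -7 and both cisplatin and radiation on Day 1.

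**If cisplatin cannot be given.** Section 5.6.2 prohibits "Chemotherapy not specified in this protocol" and says that subjects who, in the investigator's assessment, "require the use of any of the aforementioned treatments for clinical management should be removed from the trial". Footnote 2 of the section 6 flow chart adds: "If treatment is delayed beyond that window, treatment for that scheduled course must be held". The window for the weekly cisplatin visits is +/-2 days, and no make-up dose is described.

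**The concern.** Someone who satisfies the numerical renal criterion for entry should also satisfy the numerical renal criterion for the regimen that follows. The blood counts work that way. Entry needs ANC of at least 1,500 and platelets of at least 100,000, whereas cisplatin needs only more than 1,000 and more than 75,000. For creatinine the order can reverse.

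These patients are treated with curative intent, and the protocol classes cisplatin as standard of care. A patient with a stable creatinine of 1.6 mg/dL or more who enters through Table 1 receives an experimental dose first. The cisplatin rule applies only afterwards. That patient then continues on radiation and pembrolizumab without concurrent chemotherapy for as long as the hold lasts, or leaves the trial to receive other chemotherapy after one dose of study drug. The conflict could have been seen at screening.

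**Working it through.** The plan states no figure for this point, so there is nothing to reproduce. The check compares the two thresholds.

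**Inputs from the protocol**
- Entry: creatinine at most 1.5 x ULN, or clearance at least 60 mL/min (Table 1).
- Dosing: creatinine below 1.6 mg/dL (section 5.2.1.2.2).
- Planned cisplatin: six weekly doses of 40 mg/m2 (Table 2).

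**Assumptions**
- ULN between 0.9 and 1.4 mg/dL.
- Cockcroft-Gault for calculated clearance, because the footnote to that entry is not in the text available.

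**Creatinine route.** The entry limit reaches the dosing limit when 1.5 x ULN = 1.6, so the break-even ULN is 1.6/1.5 = 1.067 mg/dL.

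| Assumed ULN (mg/dL) | Entry limit, 1.5 x ULN | Creatinine values that qualify but bar cisplatin |
|---|---|---|
| 0.9 | 1.35 | none |
| 1.0 | 1.50 | none |
| 1.1 | 1.65 | 1.60 to 1.65 |
| 1.2 | 1.80 | 1.60 to 1.80 |
| 1.3 | 1.95 | 1.60 to 1.95 |
| 1.4 | 2.10 | 1.60 to 2.10 |

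**Clearance route.** This has no creatinine ceiling, so it is looser than the dosing rule at any ULN. To see whether it can realistically be met, set Cockcroft-Gault for a man, (140 - age) x weight / (72 x creatinine), equal to 60. The minimum weight is 60 x 72 x creatinine / (140 - age); for a woman, divide by 0.85.

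| Creatinine (mg/dL) | Sex | Age 45 | Age 55 | Age 65 |
|---|---|---|---|---|
| 1.6 | Man | 72.8 kg | 81.3 kg | 92.2 kg |
| 1.6 | Woman | 85.6 kg | 95.7 kg | 108.4 kg |
| 1.8 | Man | 81.9 kg | 91.5 kg | 103.7 kg |

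For example, a man aged 50 weighing 90 kg with creatinine 1.7 has a clearance of 90 x 90 / (72 x 1.7) = 66 mL/min. He meets Table 1 and cannot be given cisplatin at that creatinine.

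**Dose lost.** The planned total is 6 x 40 = 240 mg/m2. Each held week loses 40/240 = 16.7%, three lose 50% and six lose 100%. The hold is reassessed on the labs for each dose, so a later value below 1.6 allows dosing again.

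**Table 3.2.** Its 80% and 60% dose levels for peaks above 1.6 apply to transient rises. They do not override the hold for a creatinine that stays raised.

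**The case against.** The strongest reply is that Table 1 is only one part of eligibility. Inclusion 3 requires suitability for curative-intent chemoradiation, which here means cisplatin. Exclusion 15 lets the investigator exclude a patient for a laboratory abnormality that would interfere with full participation. Section 7.1.3 requires labs to be judged acceptable before every dose, including the Day -7 dose. An attentive investigator would probably catch the case. That stands as a reason to expect few patients, but all three guards rest on judgement and none states the 1.6 limit. In a multi-site trial a fixed dosing limit should not depend on each site making the connection.

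Two further safeguards exist. Interruptions of more than a week require consultation with the principal investigator (section 7.1.1.8), and most subjects who discontinue for reasons other than adverse events or progression are replaced (section 5.10). Both act only after pembrolizumab has been given. It is also fair that a cisplatin hold does not itself trigger removal; under section 5.6.2 that follows only if the investigator judges that a prohibited treatment is required.

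Some limits on the evidence stand. At an assumed ULN of 1.0 mg/dL or below, the creatinine route is the stricter rule and only the clearance route leaves a gap. The body weights depend on an assumed formula, and measured clearance or GFR is also allowed. The documents give no frequency.

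Finally, the two rules could instead be aligned by adding a clearance alternative to section 5.2.1.2.2. That is possible, but it would relax a cisplatin safeguard.

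**Conclusion.** The concern holds, as a minor point. Taken as a whole, the renal criterion is looser than the cisplatin limit at every ULN, because its clearance route has no creatinine ceiling; that conclusion needs no assumption. The creatinine route adds to the gap only where the local ULN is about 1.07 mg/dL or more. An affected patient loses 16.7% of planned cisplatin per held week, up to all of it if creatinine never falls below 1.6. The number affected cannot be estimated from the documents and is probably small. Any effect on the complete response tests is at most small and likely conservative, and no loss of power is claimed. What is at stake is protection of the individual patient and consistency of the regimen.

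**What to change.** Add one line to the renal row of Table 1:

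> The most recent serum creatinine before the Day -7 pembrolizumab dose must also be <1.6 mg/dL (the section 5.2.1.2.2 limit), whichever renal route is used.

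Flow chart footnote 15 settles which value governs: "Screening labs completed within 7 days (168 hours) of treatment initiation (day -7) will not need to be repeated". So it is the Day -7 result if labs are repeated, and otherwise the screening result from the preceding 7 days. The dosing rule stays unchanged. The new line cannot guarantee a value below 1.6 on Day 1, so section 5.2.1.2.2 still governs each cisplatin dose.

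No new test is needed, since creatinine is already measured and reviewed before the Day -7 dose. The cost is a few more screen failures and a narrower clearance route. That route would matter only at laboratories with a ULN below about 1.07 mg/dL: for creatinine above 1.50 and below 1.60 at a ULN of 1.0, or above 1.35 and below 1.60 at a ULN of 0.9.

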## 5.1.3 Subject Exclusion Criteria

The subject must be excluded from participating in the trial if the subject:

1. Patients may not be receiving any other investigational agents, chemotherapy, immunotherapy, radiotherapy, or molecular targeted agents within 4 weeks of the start of the study treatment.

- 2. Prior treatment with radiation to the head and neck
- 3. Patients with TNM Stage IVC disease
- 4. Is currently participating and receiving study therapy or has participated in a study of an investigational agent and received study therapy or used an investigational device within 4 weeks of the first dose of treatment.
- 5. Has a diagnosis of immunodeficiency or is receiving systemic steroid therapy or any other form of immunosuppressive therapy within 7 days prior to the first dose of trial treatment.
- 6. Has a known history of active TB (Bacillus Tuberculosis)
- 7. Hypersensitivity to pembrolizumab or any of its excipients.
- 8. Has had a prior anti-cancer monoclonal antibody (mAb) within 4 weeks prior to study Day 1 or who has not recovered (i.e.,  $\leq$  Grade 1 or at baseline) from adverse events due to agents administered more than 4 weeks earlier.
- 9. Has had prior chemotherapy, targeted small molecule therapy, or radiation therapy.
- 10. Has a known additional malignancy that is progressing or requires active treatment. Exceptions include basal cell carcinoma of the skin or squamous cell carcinoma of the skin that has undergone potentially curative therapy or in situ cervical cancer.
- 11. Has known active central nervous system (CNS) metastases and/or carcinomatous meningitis.
- 12. Has active autoimmune disease that has required systemic treatment in the past 2 years (i.e. with use of disease modifying agents, corticosteroids or immunosuppressive drugs). Replacement therapy (eg., thyroxine, insulin, or physiologic corticosteroid replacement therapy for adrenal or pituitary insufficiency, etc.) is not considered a form of systemic treatment.
- 13. Has known history of, or any evidence of active, non-infectious pneumonitis.
- 14. Has an active infection requiring systemic therapy.
- 15. Has a history or current evidence of any condition, therapy, or laboratory abnormality that might confound the results of the trial, interfere with the subject's participation for the full duration of the trial, or is not in the best interest of the subject to participate, in the opinion of the treating investigator.
- 16. Has known psychiatric or substance abuse disorders that would interfere with cooperation with the requirements of the trial.

- 17. Is pregnant or breastfeeding, or expecting to conceive or father children within the projected duration of the trial, starting with the pre-screening or screening visit through 120days after the last dose of trial treatment.
- 18. Has received prior therapy with an anti-PD-1, anti-PD-L1, or anti-PD-L2 agent.
- 19. Has a known history of Human Immunodeficiency Virus (HIV) (HIV 1/2 antibodies).
- 20. Has known active Hepatitis B (e.g., HBsAg reactive) or Hepatitis C (e.g., HCV RNA [qualitative] is detected).
- 21. Has received a live vaccine within 30 days of planned start of study therapy. Note: Seasonal influenza vaccines for injection are generally inactivated flu vaccines and are allowed; however intranasal influenza vaccines (e.g., Flu-Mist®) are live attenuated vaccines, and are not allowed.

#### 5.2 **Trial Treatments**

The treatment to be used in this trial is outlined below in Table 2.

Drug	Dose	Dose Frequency	Route	Regimen	Use
Pembrolizumab	200 mg	Days -7, 15, 36, 57, 78, 99, 120, 141	Intravenous	Every 3 weeks starting on day - 7 during CRT; then every 3 weeks following CRT ending on day 141.	Experimental
Cisplatin	40 mg/m2	Days 1, 8, 15, 22, 29, 36	Intravenous	Weekly starting on day 1	Standard of care
Radiation	2 Gy	Daily (Monday- Friday) starting on day 1	3D or IMRT	Day1-50 (approximate*) for a total of 35 treatments	Standard of care

 Table 2
 Trial Treatments

\*Note: If the subject experiences radiation treatment delays the active treatment phase can extend beyond 7 weeks.

Study treatment begins on day -7 with a loading dose of pembrolizumab. Day 1 signifies the start date of CRT. Both cisplatin and radiation should begin on day 1. CRT will end on the last day of radiation, which is when the cumulative dose reaches 70 Gy.

Patients will be closely monitored for treatment-related adverse events, especially hypersensitivity reactions, during the infusion and the post-infusion per local guidelines. For the duration that patients are on study therapy, adverse event monitoring will be done and recorded. Patients will be evaluated for adverse events at each visit and are to be instructed to call their physician to report any clinically significant adverse events between visits.

The site investigator shall take responsibility for and shall take all steps to maintain appropriate records and ensure appropriate supply, storage, handling, distribution and usage of trial treatments in accordance with the protocol and any applicable laws and regulations.

